6.2.3. Medication History

All current medications (prescription and over-the-counter) taken at Screening, 90 days prior to Screening, and throughout the course of the study will be recorded in the Concomitant Medications page of the eCRF. Information regarding the dates of first and last dose, site of dosing (e.g., right eye, left eye, OU, systemic), and the reason the medication is being taken must be recorded in the eCRF.

6.2.4. Urine Pregnancy Test

A urine pregnancy test will be performed at Visit 1/Screening and Visit 2/Day 1 and repeated at Visit 7/Day 84 or the Early Discontinuation Visit for women of childbearing potential only.

6.3. Efficacy Assessments

Efficacy will be measured by assessment of DED symptoms (SANDE total score, individual symptoms rated on a visual analogue scale (VAS): itching, foreign body sensation, burning/stinging, fluctuating vision, eye dryness, eye discomfort, photophobia, and eye pain) and signs (TBUT, Schirmer's test [anesthetized], corneal fluorescein staining, conjunctival lissamine green staining, and conjunctival hyperemia). All efficacy assessments will be conducted at the timepoints shown on the Schedule of Visits and Examinations (Table 1).

6.3.1. Symptoms

[figure not shown]
6.3.1.1. SANDE (Symptom Assessment in Dry Eye) Questionnaire

The SANDE contains two questions regarding the frequency and severity of DED symptoms as shown in Figure 1.

Figure 1: Symptom Assessment in Dry Eye (SANDE) Questionnaire

[figure not shown]
1. Frequency of symptoms:

Please place a mark on the line to indicate how often, on average, your eyes feel dry and/or irritated:

2. Severity of symptoms:

Please place a mark on the line to indicate how severe, on average, you feel your symptoms of dryness and/or irritation are:

Source: [Schaumberg et al., 2007](#)

The frequency and severity scores (SANDE) will be recorded in the eCRF. The total score is the square root of the frequency score times the square root of the severity score (range 0-100) and will be calculated by the electronic data capture (eDC) system.

6.3.1.2. Measurement of Individual Dry Eye Symptoms

The following individual symptoms of DED will be evaluated using a separate VAS scale for each symptom and will include: itching, foreign body sensation, burning/stinging, fluctuating vision, eye dryness, eye discomfort, photophobia, and eye pain.

The subject will be asked to make a mark on the line to indicate how he/she feels about each symptom since the last visit.

Itching

Doesn't itch at all

Want to scratch my eyes out

Foreign Body Sensation

Don't feel like I have something in my eye

Feel like I have sand in my eye

Burning/Stinging

Doesn't burn/sting at all

Severe

Fluctuating Vision

Vision is fine

[figure not shown]
Vision constantly changes

Eye Dryness

[figure not shown]
Not dry at all

Extremely dry

Eye Discomfort

Photophobia

Eve Pain

The score for each symptom will be recorded in the eCRF.

[figure not shown]
6.3.2. Signs

6.3.2.1. Tear Break-up Time

The tear film will be observed under the slit-lamp and timed until the tear film breaks up (i.e., tiny dry spots develop) (Nichols et al., 2004). The procedure is conducted 2 times for each eye and the TBUT for each is measured in seconds and recorded in the eCRF. The average for each eye will be calculated by the eDC system. Consult the Study Reference Manual for specific details regarding the evaluation procedures.

6.3.2.2. Corneal Fluorescein Staining

Following evaluation of TBUT, corneal fluorescein staining using a Wratten #12 filter (or equivalent) will be measured using the National Eye Institute (NEI) standardized grading system to grade each of the 5 areas of the cornea on a 0-3 scale (as shown in [Figure 2](#)) (range: 0 – 15) ([Lemp, 1995](#)). Consult the Study Reference Manual for specific details regarding the evaluation procedures.

Figure 2: Division of the Corneal Surface for Measuring Fluorescein Uptake

[figure not shown]
Source: [Lemp, 1995](#)

6.3.2.3. Conjunctival Hyperemia

Conjunctival hyperemia will be graded during the slit-lamp examination using the McMonnies photographic scale ([McMonnies and Chapman, 1987a](#); [McMonnies and Chapman, 1987b](#)). This photographic reference scale consists of 6 levels or grades of conjunctival hyperemia (0 = none, 5 = severe). Please note that these were designed for contact lens wearers, but validated for non-contact lens wearers ([McMonnies and Ho, 1991](#)). Consult the Study Reference Manual for specific details regarding the evaluation procedures.

6.3.2.4. Conjunctival Lissamine Green Staining

After corneal staining, lissamine green conjunctival staining will be measured. Six (6) areas of the conjunctiva will be evaluated ([Figure 3](#)) ([Lemp, 1995](#)). The Investigator will record a score for each area of each eye. The scores for each eye will be summed, excluding superior zones 2 and 4. Consult the Study Reference Manual for specific details regarding the evaluation procedures.

Figure 3: Division of the Conjunctival Surface for Measuring Lissamine Green Staining

6.3.2.5. Anesthetized Schirmer's Test

An anesthetized Schirmer's test will be performed at least 5 minutes after the lissamine green conjunctival staining to allow for any reflex tearing to subside ([Li et al., 2012](#); [Tsubota et al., 1999](#)). Following instillation of topical anesthetic, filter paper strips will be placed in both eyes inside the lower eyelid (conjunctival sac) at the same time. The eyes are closed for 5 minutes. The paper is then removed and the amount of moisture on each strip in

millimeters (mm) is measured and recorded in the eCRF ([Wolffsohn et al., 2017](#)). Consult the Study Reference Manual for specific details regarding the evaluation procedures.

6.4. Adverse and Serious Adverse Events

6.4.1. Definition of Adverse Events

6.4.1.1. Adverse Event (AE)

An AE is any untoward medical occurrence in a clinical study subject administered an IP that does not necessarily have a causal relationship with this treatment. An AE can therefore be any unfavorable and unintended sign (for example, an abnormal laboratory finding), symptom, or disease temporally associated with the use of an IP, whether or not considered related to this IP.

Note: IP in this study refers to all concentrations of SDP-4 and to the vehicle (control).

Medical conditions/diseases present before starting the investigational treatment are only considered AEs if they worsen after starting the investigational treatment. Abnormal test results constitute AEs only if they induce clinical signs or symptoms, are considered clinically significant, or require therapy.

The occurrence of AEs should be sought by open-ended questioning of the subject at each visit during the study. At each clinic visit, study personnel should ask the following question: "Have you had any problems since your last visit?" Adverse events also may be detected when they are volunteered by the subject during or between visits or through study assessments.

6.4.1.2. Serious Adverse Event (SAE)

An SAE is any untoward medical occurrence that at any dose:

- Results in death
- Is life-threatening or sight-threatening

Note: The term "life-threatening" refers to an event in which the subject was at risk of death at the time of the event; it does not refer to an event which hypothetically might have caused death if it were more severe.

- Results in persistent or significant disability/incapacity (excluding progression/outcome of the disease under study)
- Is a congenital anomaly/birth defect
- Requires inpatient hospitalization or prolongation of existing hospitalization
- Is medically significant; i.e., defined as an event that jeopardizes the health of the subject or may require medical or surgical intervention to prevent one of the outcomes listed above

Treatment on an outpatient emergency basis that does not result in hospital admission, or a hospitalization that is elective or is a preplanned treatment for a pre-existing condition that is

unrelated to the indication under study and has not worsened since the start of the study, is not considered an SAE.

All SAEs that are ongoing at the time of completion or discontinuation from the study will be followed until stabilization or resolution of the event.

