6.6. Recording Adverse Events

Adverse events (AEs) spontaneously reported by the subject and/or in response to an open question from the study personnel or revealed by observation, regardless of severity or potential association with the IP or study procedures, will be recorded in the eCRF. Changes from baseline assessments that are part of the disease being studied will not necessarily be recorded as AEs unless the Investigator deems them as such. Investigators are advised to consider reporting an increase in IOP of 10 mmHg or greater, or a visual acuity decrease of 3 lines EDTRS (15 letters) or greater as an AE. If ongoing at the time of the subject's last study visit, Investigators should follow the event until the subject has returned to baseline or the event has resolved.

All AEs that occur following consent and until the final study visit (Visit 7/Day 84) should be collected and recorded on the AE eCRF page. AEs that occur during the screening/run-in period (Visit 1/Day-14 ± 2 to Visit 2/Day 1) will be summarized separately from AEs that occur from the first dose of double-masked treatment on Day 1 to the Day 84 Visit or Early Discontinuation. Serious adverse events (SAEs) will be followed until the event is resolved or stabilized.

The AE term should be reported in standard medical terminology when possible. For each AE, the Investigator will evaluate and report the following:

- Onset (date)
- Resolution (date)
- Severity grade (mild, moderate, severe)
- Relationship to IP (not suspected, suspected)
- Action taken (none, IP temporarily interrupted, IP permanently discontinued; concomitant medication taken; hospitalization/prolonged hospitalization; other)
- Serious outcome (yes/no)

The severity grade should be determined by the Investigator using the definitions below:

- **Mild:** Discomfort noticed but no disruption of normal daily activity
- **Moderate:** Discomfort sufficient to cause interference with normal daily activity
- **Severe:** Incapacitating, with inability to perform normal activities

It is important to distinguish between serious and severe AEs. Severity is a measure of intensity (as defined directly above) whereas seriousness is defined by the criteria under Section 6.4.1.2. An AE of severe intensity may not be considered serious.

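### Protocol Section 6.4.1.2 contradicts itself on whether a serious event treated as an outpatient emergency, without admission, counts as an SAE

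*Protocol*

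**What the plan says.** Section 6.4.1.2 opens with "An SAE is any untoward medical occurrence that at any dose" and then gives six bullets, any one of which is enough. Three matter here:

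- "Is life-threatening or sight-threatening"
- "Requires inpatient hospitalization or prolongation of existing hospitalization"
- "Is medically significant; i.e., defined as an event that jeopardizes the health of the subject", a bullet that goes on to include an event that "may require medical or surgical intervention to prevent one of the outcomes listed above"

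After the bullets comes one sentence with two limbs. The first limb is "Treatment on an outpatient emergency basis that does not result in hospital admission". The second is an elective hospitalization, or a preplanned one for a pre-existing condition. The sentence ends: "unrelated to the indication under study and has not worsened since the start of the study, is not considered an SAE".

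Section 6.6 separates severity from seriousness and says that "seriousness is defined by the criteria under Section 6.4.1.2". Section 6.7 attaches 24-hour reporting, the SAE form, notification of the IRB and sponsor reporting to the FDA to SAE status. Section 9.6.2 gives SAEs their own summary.

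**The concern.** The list defines seriousness by what the event is or leads to. The closing sentence declares something not to be an SAE because of where it was treated. An event can satisfy the first and fall under the second, and the section does not say which prevails.

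The overlap is closest with the medically significant criterion. An event needing intervention to avert a worse outcome is the sort of event that may be treated urgently and sent home. The sight-threatening criterion is exposed in the same way, since nothing in it presupposes admission.

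At stake is timely safety reporting. The Introduction (Section 1) describes this as the first study of SDP-4 in humans, and Section 3.1 has both eyes dosed for 84 days. If a site takes the closing sentence at its word, the 24-hour clock does not start for such an event, and the event is absent from the SAE summary.

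**Working it through.** No arithmetic applies, and the protocol states no figure to reproduce. The check is to apply the two parts of Section 6.4.1.2 to the same events and then look for a passage that decides between them.

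**Step 1: what the list requires.** Of the six criteria, only the hospitalization bullet mentions admission. The life- or sight-threatening bullet and the medically significant bullet can both be met by a subject who is never admitted.

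**Step 2: what the closing sentence excludes.** The conditions about being unrelated to the indication and not having worsened follow the hospitalization limb and describe the pre-existing condition named there. They do not restrict the outpatient limb. That limb is limited only by its own terms: emergency basis, outpatient, no admission.

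**Step 3: apply both parts.**

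| Event | By the list | By the closing sentence, read literally | Agree? |
|---|---|---|---|
| Outpatient emergency treatment, no criterion met | Not an SAE | Not an SAE | Yes |
| Judged sight-threatening, treated as an outpatient emergency | SAE | Not an SAE | No |
| Judged life-threatening or medically significant, treated in an emergency department and discharged | SAE | Not an SAE | No |
| Judged sight-threatening, treated as an outpatient but not as an emergency | SAE | Sentence does not apply | No conflict |
| Emergency leading to admission | SAE | Outpatient limb does not apply | No conflict |

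The conflict is confined to rows two and three. Both depend on the investigator judging that the criterion is met.

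**Step 4: look for a tie-breaker.**

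- Section 6.6 refers seriousness back to the criteria in Section 6.4.1.2, the section that contains the conflict. It leans towards the bullets but does not override the closing sentence.
- The yes/no item on seriousness that Section 6.6 requires for each AE is answered from that same definition, so it is not an independent check.
- Section 6.7 begins from events already classed as SAEs.

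No passage says that the list prevails.

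**Step 5: look at where the sentence is placed.** Where Section 6.4.1.2 limits a single criterion elsewhere, it does so at that criterion: the disability bullet carries its exclusion in parentheses, and the note explaining life-threatening sits directly under its bullet. The closing sentence instead follows all six bullets, and its conclusion is about SAE status, not about the hospitalization criterion.

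**The case against.** The best defence is that the closing sentence only clarifies the hospitalization bullet. Its grammatical subjects are a treatment and a hospitalization, not an occurrence, and both limbs concern admission. On that reading a sight-threatening event treated in an emergency department remains an SAE. Section 6.6 helps this reading by pointing to the criteria, and so does the medically significant bullet by expressly covering events that need intervention. This is plausible and may well be what was meant. But it has to be supplied by the reader. A treatment is not itself an untoward occurrence, so the sentence does little unless it classifies the event being treated.

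A second defence is that the events stay visible, and this stands. Section 6.6 has every AE recorded with severity, relationship, action taken and the seriousness item. Section 10.5 has monitors review data as entered and refer safety signals to the Medical Monitor. Section 9.6.2 tabulates TEAEs, including by severity and relationship. None of these starts the 24-hour clock, but together they make the realistic failure a late or misclassified report, not a lost event.

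A reader might go further and infer that life-threatening, sight-threatening and medically significant events treated without admission simply fall outside SAE reporting. The document does not support that. The list still makes them SAEs, the narrower reading is available, and the excluded phrase covers emergency outpatient treatment only, not all outpatient care.

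**Conclusion.** The contradiction is real and lies within one section. For an event that meets the life-threatening, sight-threatening or medically significant criterion and is treated as an outpatient emergency without admission, the list says SAE and the closing sentence, taken literally, says not. Sites could classify the same event differently, and some could fail to report it within 24 hours or leave it out of the SAE summary.

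The size cannot be given as a number. The protocol states no expected rate for such events and no indication of how sites would read the sentence. No endpoint, power calculation or efficacy analysis is affected. The conclusion rests on two points: the outpatient limb has no proviso, and no other section supplies one. It is worth correcting because the definition controls expedited reporting in a first-in-human study, and the words as written, not merely missing detail, cause the conflict.

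**What to change.** Amend the closing sentence of Section 6.4.1.2 so that both limbs are tied to the hospitalization criterion. Suggested wording: *Emergency care given without admission, and an elective or preplanned hospitalization for an unrelated pre-existing condition that has not worsened, do not by themselves meet the hospitalization criterion. An event that meets any other criterion listed above remains an SAE.* Put the same wording in the SAE form guidance, so that the seriousness item in Section 6.6 is answered on the same basis at every site.

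The cost is a short protocol amendment and an update to the form guidance. The downside is that a few more events may enter 24-hour reporting. Visits, endpoints and analyses are unchanged.

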6.5. Relationship to Investigational Product

The relationship of AEs to the IP should be assessed by the Investigator using the definitions below.

Not suspected: The temporal relationship of the event to the IP makes a causal relationship unlikely, or, other drugs, therapeutic interventions or underlying conditions provide a sufficient explanation for the observed event.

Suspected: The temporal relationship of the event to the IP makes a causal relationship possible or other drugs, therapeutic interventions or underlying conditions do not provide a sufficient explanation for the observed event.

If there is any valid reason, even if undetermined, for suspecting a possible cause-and-effect relationship between the IP and the occurrence of the AE, then the AE should be considered “suspected.”

If the relationship between the AE/SAE and the IP is determined by the Sponsor to be “suspected” the event will be considered to be related to the IP for the purposes of expedited regulatory reporting.

6.6. Recording Adverse Events

Adverse events (AEs) spontaneously reported by the subject and/or in response to an open question from the study personnel or revealed by observation, regardless of severity or potential association with the IP or study procedures, will be recorded in the eCRF. Changes from baseline assessments that are part of the disease being studied will not necessarily be recorded as AEs unless the Investigator deems them as such. Investigators are advised to consider reporting an increase in IOP of 10 mmHg or greater, or a visual acuity decrease of 3 lines EDTRS (15 letters) or greater as an AE. If ongoing at the time of the subject's last study visit, Investigators should follow the event until the subject has returned to baseline or the event has resolved.

All AEs that occur following consent and until the final study visit (Visit 7/Day 84) should be collected and recorded on the AE eCRF page. AEs that occur during the screening/run-in period (Visit 1/Day-14 ± 2 to Visit 2/Day 1) will be summarized separately from AEs that occur from the first dose of double-masked treatment on Day 1 to the Day 84 Visit or Early Discontinuation. Serious adverse events (SAEs) will be followed until the event is resolved or stabilized.

The AE term should be reported in standard medical terminology when possible. For each AE, the Investigator will evaluate and report the following:

- Onset (date)
- Resolution (date)
- Severity grade (mild, moderate, severe)
- Relationship to IP (not suspected, suspected)
- Action taken (none, IP temporarily interrupted, IP permanently discontinued; concomitant medication taken; hospitalization/prolonged hospitalization; other)
- Serious outcome (yes/no)

The severity grade should be determined by the Investigator using the definitions below:

- **Mild:** Discomfort noticed but no disruption of normal daily activity
- **Moderate:** Discomfort sufficient to cause interference with normal daily activity
- **Severe:** Incapacitating, with inability to perform normal activities

It is important to distinguish between serious and severe AEs. Severity is a measure of intensity (as defined directly above) whereas seriousness is defined by the criteria under Section 6.4.1.2. An AE of severe intensity may not be considered serious.

Should a pregnancy occur, it must be reported and recorded on the pregnancy form. Pregnancy in itself is not regarded as an AE unless there is a suspicion that an IP may have interfered with the effectiveness of a contraceptive medication. The subject will stop using the IP, be withdrawn from the study, and followed through conclusion of pregnancy. The outcome of all pregnancies (spontaneous miscarriage, elective termination, normal birth or congenital abnormality) must be followed up and documented.

6.7. Reporting Adverse Events

All AEs (suspected and not suspected) will be recorded following consent and until the final study visit, Visit 7/Day 84. Any SAEs “suspected” to be related to the IP and discovered by the Investigator at any time after the study should be reported.

Any SAE that occurs must be reported within 24 hours of its occurrence or within 24 hours of learning of its occurrence by entering the information in the appropriate eCRF page in the EDC system. Recurrent episodes, complications, or progression of the initial SAE must be reported as follow-up to the original episode within 24 hours of the Investigator receiving the information. Information about all SAEs will be collected and recorded on the SAE form. All pertinent medical records and information collected during the treatment and follow-up of the subject should be maintained at the site with a copy emailed to [contact] only if requested and after thorough de-identification/ removal of all personal health information (PHI). The Investigator must assess the SAE relationship to the IP/study treatment and severity and complete the SAE form. Silk Technologies/Oculos may request additional information. Follow-up information (e.g.,

discharge summary) will be retained in the subject's chart and a copy will be emailed to [contact].

In addition, all SAEs should be recorded on the Adverse Event eCRF page with the serious question marked "Yes".

All subjects who experience an SAE should be followed clinically and undergo the appropriate diagnostic evaluations until stabilization or resolution of the event.

It is the Investigator's responsibility to notify the approving IRB of any site-specific SAEs per the IRB's reporting requirements.

Silk Technologies will report all SAEs to the United States (US) Food and Drug Administration (FDA) on the appropriate schedule depending if the event is IP related or not IP related, expected or unexpected (based on the available information in the [IB](#)).

Any death occurring during the study and follow up period should be reported as an SAE. For any death occurring through the end of the study, regardless of the degree of relationship to IP, the SAE resulting in the death must be reported to Silk Technologies or designee. A death occurring after completion of the study does not require completion of the SAE form.

